3.1. Overall Design

3.2. Sample Size and Power

There will be 4 stages in the study: in the first stage, subjects will be randomly assigned to placebo or the lowest dose (CCI) until at least 10 subjects have been recruited. In the second stage, up to 30 subjects will be randomly assigned to a placebo or CCI of MEDI7352; prior to commencing the third stage, the safety and tolerability experience following administration of multiple doses of CCI in the Phase 1 study of MEDI7352 will be evaluated. In stage 3 of the study, approximately 67 subjects will be randomly assigned to placebo or CCI of MEDI7352. The third stage will include an interim analysis to enable decision making for stage 4 with respect to the sample size and dose allocation ratio. If no changes are made following the interim analysis, in stage 4 of the study, approximately 165 eligible subjects will be randomly assigned to treatment across 3 dose levels of MEDI7352 (CCI) or placebo, to ensure that approximately 236 subjects are evaluable for the efficacy analysis of stages 2 to 4 combined. The number of subjects in the fourth stage is currently planned to follow an equal treatment allocation to each of the 4 treatment groups. However, the exact number of subjects and the allocation to each dose in stage 4 will be determined after the interim analysis.

There is no formal sample size calculation for stage 1; 10 subjects in stage 1 are considered sufficient for the initial assessment of safety. The sample size for stages 2-4 combined was determined by a formal power calculation (see below) and the size of stage 3 was defined to enable decision making for the stage 4 sample size and dose allocation ratio.

This study is powered at greater than 80% to detect a statistically significant (1-sided alpha = 0.025) dose-response relationship when the true Week 12 placebo-corrected change from baseline difference at the $\boxed{\text{CCI}}$ dose is 1.25 on the 11-point NRS scale (MEDI7352-placebo treatment) and the true dose-response follows a hyperbolic Emax relationship, with ED50 within the range 1-750 µg/kg. This calculation also assumes:

- The true standard deviation (SD) is 2.4, which is based on other studies undertaken with pregabalin in PDN (Satoh et al. 2011, Lesser et al. 2004, Rosenstock et al. 2004, Tölle et al. 2008).

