- The data from stages 2, 3, and 4 are combined so that the number of subjects for the dose-response analysis is 236 with the total number evaluable for placebo, column doses equal to 81, 37, 51, and 67, respectively. This is comprised of, assuming an overall 10% non-evaluability rate:
 - o 28 out of 30 randomised in stage 2; 14 per arm
 - o 60 out of 67 randomised in stage 3; 30 per arm, and
 - o 148 out of 165 randomised in stage 4; 37 per arm
- The dose-response hypothesis test is multiplicity adjusted as described by Pinheiro et al. 2006 in order to control the type 1-error.

The above calculations were performed using the software R and the R-package 'DoseFinding' [https://cran.r-project.org/web/packages/DoseFinding/DoseFinding.pdf] with the following parameters:

- Population SD (of change from baseline to week 12) = 2.4
- Placebo effect = 1 point reduction in NRS and CCl effect = 2.25 reduction from baseline, ie, delta= 1.25
- Linear contrasts were determined from 5 'candidate dose' response models which are all E_{max} models with decreasing potency/increasing ED50: 7.5, 15, 30, 60, 750 μg/kg. The 5th case is essentially linear in dose. E_{max} models were chosen following the recommendations in a recent meta-analysis of dose response studies by Thomas et al., 2014.
- Power was assessed across 16 alternative true dose response curves, 12 E_{max} with ED50 ranging from 0.375 to 750 μg/kg, 3 logistic and 1 quadratic, all having a Week 12 placebo-corrected change from baseline difference at the column dose of 1.25.

[figure not shown]
The overall withdrawal rate is anticipated to be approximately 10%. However, since the primary analysis will use Last Observation Carried Forward (LOCF) for withdrawn subjects, and the SD estimate is taken from studies which also used the LOCF approach, the only additional subjects recruited will be to account for withdrawals in stages 2, 3, and 4 if withdrawal occurs at, or prior to, the Week 2 visit.

The number of subjects who will agree to participate in the genetic research is unknown. It is therefore not possible to establish whether sufficient data will be collected to allow a formal statistical evaluation or whether only descriptive statistics will be generated.

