2. Equations for Dose (ED_P) to achieve a certain proportion P of the effect of the maximum dose studied versus placebo (See DoseFinding manual page 51 where ED is 'Effective Dose')

Emax: $ED_P = (P * ED_{50} * max(doses))/(ED_{50} + (1-P) * max(doses)) = (P * ED_{50} * 150)/(ED_{50} + (1-P) * 150)$

[figure not shown]
Exponential: $ED_P = \delta * log((P*exp(max(doses)/\delta) + 1-P)) = \delta * log((P*exp(150/\delta) + 1-P))$

(The function ED from the DoseFinding package will be used for the above)

3. Equation for Dose (asym ED_P) to achieve a certain proportion P of the asymptotic maximum effect (E_{max}) versus placebo

Emax: asymptotic $ED_P = (P*ED_{50})/(1-P)$

Simulation-based CI will be created for each of the above quantities from the mean and covariance matrix of the model parameters, assuming multivariate normality. Therefore 10,000 samples from the multivariate distribution will be taken, and for each simulation the TD and ED estimates calculated. The 2.5% and 97.5% percentiles will then form the appropriate 95% two-sided CI.

[figure not shown]

Sponsor:	AstraZeneca
Protocol Title	A Randomised, Double-Blind, Placebo-Controlled, Dose- Response Study of the Efficacy and Safety of MEDI7352 in Subjects with Painful Diabetic Neuropathy
Development Phase	2
Protocol Numbers:	D5680C00002
Premier Research PCNs:	MEDU177093
Document Version:	Final Version 1.0
Document Date:	12-Jul-2023

Document History

Version	Date	Author	Description
0.1	24-Mar-2023	PPD	Draft Version
0.2	21-Apr-2023	PPD	Draft Version
0.3	24-May-2023	PPD	Draft Version
0.4	20-Jun-2023	PPD	Draft Version

Final 1.0 | 12-Jul-2023 | Page 1 of 205

Tables, Listings, and Figures Conventions

All listings, tables, and graphs will have a header showing the sponsor company name, protocol and version of delivery and a footer showing the version of SAS, the file name and path, and the source of the data (listing number).

The following reporting conventions will be adopted for the presentation of study data. These conventions will enhance the review process and help to standardize the presentation with common notations.

[figure not shown]
General Reporting Conventions

- All tables and data listings will be developed in landscape orientation.
- Specialized text styles, such as bolding, italics, borders, shading, and superscripted and subscripted text will not be used in tables, figures, and data listings unless they add significant value to the table, figure, or data listing.

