'MOD' step [3] Selected Model xxxxxxxxx

Parameter	Estimate	95% CI of Estimate [6]
ED50	XX.X	[x.xx to x.xx]
ED90 [4]	XX.X	[x.xx to x.xx]
Asymptotic ED90 [5]	XX.X	[x.xx to x.xx]
Dose to achieve target (-1.25) effect	XX.X	[x.xx to x.xx]
Treatment effect at dose = 5 mcg	XX.X	[x.xx to x.xx]
Treatment effect at dose = 50 mcg	XX.X	[x.xx to x.xx]
Treatment effect at dose = 150 mcg	XX.X	[x.xx to x.xx]
Treatment effect at dose = 450 mcg	xx.x	[x.xx to x.xx]

CI: Confidence Interval; LOCF = Last Observation Carried Forward; MCP = Multiple Comparisons; Procedure; MOD = Modelling; NRS = Numeric rating scale.

Programming Notes:

• The 'MOD' step will only be performed if stage 4 is initiated, otherwise there would be insufficient dosing data to fit the non-linear models.

Final 1.0 | 12-Jul-2023 | Page 27 of 205

^[3] Results from the 'MOD' step will only be available in case any of the MCP tests is statistically significant.

^[4] ED90 = Effective Dose giving 90% of the effect of the maximum dose studied.

^[5] Asymptotic ED90 = Effective Dose giving 90% of the asymptotic maximum effect.

^{[6] 2.5%} and 97.5% quantiles taken from 100000 samples from the multivariate normal distribution for model fitted estimates and its covariance matrix. Reference Listing: 16.2.6.1

[figure not shown]

Table 14.2.1.2.2 Statistical Analysis of CFB to Week 12 Daily Pain NRS: Primary ANCOVA Analysis (LOCF) mITT Population

Model parameter estimates

					2-sided 95% unadjusted Asymmetric CL		2-sided
Parameter	Estimate	t value	Degrees of freedom	Standard Error	CL	[1]	P-value [2]
Intercept	XX.XX	XX.XX	•	xx.xxx	[x.xx to x.xx]		
Co-Medication Type			2				0.xxxx
Baseline pain NRS	XX.XX	XX.XX	1	XX.XXX	[x.xx to x.xx]		0.xxxx
Active 5 mcg vs Placebo	XX.XX	XX.XX	1	XX.XXX	[x.xx to x.xx]	[x.xx to x.xx]	0.xxxx
Active 150 mcg vs Placebo	XX.XX	XX.XX	1	XX.XXX	[x.xx to x.xx]	[x.xx to x.xx]	0.xxxx
Active 450 mcg vs Placebo	XX.XX	XX.XX	1	XX.XXX	[x.xx to x.xx]	[x.xx to x.xx]	0.xxxx
Model residual standard deviation	XX.XX						

ANCOVA = analysis of covariance; CFB = Change from Baseline;

CL = Confidence limits; LOCF = Last Observation Carried Forward; NRS = Numeric rating scale.

[2] P-value is derived from the following model: ANCOVA by dose using NRS baseline value and co-medication as covariates, with CFB to Week 12 (LOCF) as dependent variable.

Least Square Means

Treatment	Number of Subjects	LS mean [3]	95% CI of LS mean
Active 450 mcg	XX	X.XX	[x.xx to x.xx]
Active 150 mcg	XX	X.XX	[x.xx to x.xx]

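### The confidence intervals for ED50, ED90 and the target dose come from unrestricted normal draws, with no rule for a non-positive ED50 or an unreachable target

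*SAP*

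**What the plan says.** Section 15 of SAP v1.1 (Appendix: Calculation of Dose to achieve target effects) adopts the DoseFinding package's original parametrization, so ED50 enters on the dose scale and not as a logarithm. For the Emax model it defines TD = ED50/((Emax/Δ) − 1) and ED_P = P·ED50·max/(ED50 + (1−P)·max), with the maximum dose written as 150. Intervals come from the fitted mean and covariance of the parameters under multivariate normality: "Therefore 10,000 samples from the multivariate distribution will be taken, and for each simulation the TD and ED estimates calculated". Then: "The 2.5% and 97.5% percentiles will then form the appropriate 95% two-sided CI". No bound, log scale, truncation or not-reached rule is given. Section 15 of SAP v1.0 reads the same. The section names the package functions TD and ED for the calculation but does not say how a draw without an attainable dose is handled.

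Shell Table 14.2.1.2.1 (shells v1.0, MOD step) applies the method to ED50, ED90, asymptotic ED90 and the row "Dose to achieve target (-1.25) effect". It lists treatment effects at 5, 50, 150 and 450 and refers to 100,000 samples.

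Under Section 8.1 the MOD step runs only if stage 4 is initiated and the MCP test is significant. The interim analysis plan (Section 6.1.6 and Appendix A2) does foresee a negative ED50 and switches to linear interpolation. The final analysis has no counterpart.

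**The concern.** ED50 must be positive in an Emax model. With three active doses and noisy pain scores it is poorly estimated, so a symmetric normal distribution around the estimate can put much of its mass below zero. If that share is well above 2.5%, draws that are impossible under the model set the reported limit.

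The target dose has a second fault. The 1.25 target in the shell equals the effect assumed for the sample size, so a draw with Emax below the target is an expected event. In such a draw no dose suffices, yet the formula still returns a number. These intervals state the uncertainty about dose for the secondary objective of characterising dose-response (Section 2.1.2).

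**Working it through.** **Inputs (SAP v1.1, Section 3.2).** Power: "This study is powered at greater than 80% to detect a statistically significant (1-sided alpha = 0.025". SD: "Population SD (of change from baseline to week 12) = 2.4". Effect: "effect = 2.25 reduction from baseline, ie, delta= 1.25". Group sizes, placebo first: "doses equal to 81, 37, 51, and 67, respectively"; 81 + 37 + 51 + 67 = 236. Candidate models: "decreasing potency/increasing ED50: 7.5, 15, 30, 60, 750". The target of 1.25 is from the shell.

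**Assumption.** The doses behind the group sizes are redacted. Three sets were run: 0/50/150/450 (main case), 0/5/150/450 and 0/5/50/150.

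**The plan's own figure.** Optimal contrasts for the five candidates, with a critical value of 2.18 at 0/50/150/450, give power of 88-95% for ED50 from 1 to 750. The other two sets give 90-95%. This agrees with the stated power above 80%, so the inputs are read correctly.

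**Precision of the Emax fit.** Effects are written as reductions, so Emax is positive when the drug works. With Emax = 1.25·(top + ED50)/top and a Jacobian row [1, d/(d+ED50), −Emax·d/(d+ED50)²] for each dose d, the covariance is 2.4²·(J′·diag(n)·J)⁻¹.

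Worked case, 0/50/150/450 and true ED50 60:
- Emax = 1.25 × 510/450 = 1.417.
- The ED50 column of J is 0, −0.00585, −0.00482, −0.00245. The Emax column is 0, 0.455, 0.714, 0.882.
- SE(ED50) = 88.1 and SE(Emax) = 0.535.
- P(ED50 < 0) = Φ(−60/88.1) = Φ(−0.68) = 25%.
- P(Emax < 1.25) = Φ((1.25 − 1.417)/0.535) = Φ(−0.31) = 38%.
- ED50 interval: 60 ± 1.96 × 88.1, about −113 to 232.
- TD: the true value is 60/(1.417/1.25 − 1) = 450. The percentile interval is about −2,160 to 2,500.
- ED90 with maximum 450: the true value is 0.9 × 60 × 450/(60 + 45) = 231, interval about −1,320 to 1,860. With the 150 written in Section 15 the true value is 0.9 × 60 × 150/(60 + 15) = 108, interval about −130 to 380.

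**All candidate ED50s, 0/50/150/450, effect 1.25:**

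| True ED50 | ED50 < 0 | Emax < 1.25 | Either |
|---|---|---|---|
| 7.5 | 40% | 48% | 60% |
| 15 | 33% | 46% | 56% |
| 30 | 28% | 43% | 51% |
| 60 | 25% | 38% | 45% |
| 750 | 38% | 38% | 40% |

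The Emax column includes draws with Emax of the wrong sign; for true ED50 of 150 and 300 the share is about 31%. Across the three dose sets ED50 < 0 occurs in 25-45% of draws. The ED50 lower limit was negative in every scenario.

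**Larger effect.** At 2.0 points (0/50/150/450, true ED50 30 to 150), ED50 < 0 falls to 14-17% and Emax < 1.25 to 3-5%. The first fault remains; the second nearly disappears.

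**Where draws that miss the target land.** If Emax/Δ < 1, the denominator of TD is negative. TD is then negative when ED50 > 0 and positive when ED50 < 0. At 0/50/150/450 and effect 1.25, 45-94% of these draws give a positive TD (true ED50 7.5 to 750). It passes for a valid dose although it comes from an impossible ED50.

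**Allowing for the MOD condition.** In 800 simulated trials per scenario (true ED50 7.5, 30, 60, 750; sets 0/50/150/450 and 0/5/50/150), only trials with a significant MCP test and an interior Emax fit were kept. The ED50 search range, 0.001 to 1.5 times the top dose, is an assumption. The median share of draws with ED50 < 0 was 26-31% at effect 1.25 and 15-24% at effect 2.0. Lower limits for ED50 and TD were negative in 100% of analysed trials, to rounding.

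**Check of the repair.** Drawing log(ED50) at 0/50/150/450 gives ED50 intervals of 1.1 to 812 (true 30) and 3.4 to 1,085 (true 60), and ED90 intervals of 10 to 384 and 28 to 389. The target is still missed in 43% and 38% of draws. With those ranked highest, the TD lower limits are about 20 and 43 and the upper limits are open.

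**The case against.** The doses are redacted, so any figure rests on an assumed set. That stands, which is why ranges over three sets are given; the ED50 result is the same in each.

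The MOD step follows a significant test and a choice among hyperbolic Emax, sigmoid Emax and linear. The shares at the true parameters ignore this, but the simulated trials that impose significance show the same fault. Model selection was not simulated; a linear fit has no ED50 and a sigmoid fit adds a parameter.

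The named package functions may treat an unreachable target specially. The documents do not say so, and special handling of TD would leave the ED50 interval as it is.

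The −1.25 row comes from shells v1.0. The copy of shells v1.1 at hand ends before this table, and Section 8.1 speaks only of selected target effects. The ED50 finding does not depend on the target.

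A reader might infer more than the documents support:
- That every draw missing the target is counted as a low dose. About half or more give a positive TD.
- That all limits are negative. At true ED50 750, ED90 runs from about 292 to 516 (0/50/150/450, maximum 450) and TD from about 65 to 234 (0/5/50/150).
- That the ED90 interval is necessarily in the thousands. That needs a maximum dose of 450; Section 15 writes 150.
- That a dose choice rests on these intervals. Nothing says so, and the plan also reports model effects at the studied doses and pairwise comparisons with placebo (Sections 8.1 and 8.1.1).

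**Conclusion.** The interval rule in Section 15 is wrong as written. Followed literally at the planning assumptions, 25-45% of draws have an impossible ED50, against a 2.5% tail, so those draws set the lower limit. A negative dose would then be reported as the lower bound for ED50 in every scenario run, and for TD and ED90 in most. The TD percentiles mix real doses, negative artefacts and spuriously positive ones, and have no clear meaning. A larger true effect reduces the fault without removing it.

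These sizes rest on the assumed dose sets, the hyperbolic Emax model without covariates, and the formulas as printed. The MCP test, its type I error and its power are not touched. The damage is confined to the precision statements for the dose parameters.

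**What to change.** In Section 15, obtain the intervals with ED50 constrained to be positive. Either sample log(ED50) with its covariance, or draw the adjusted dose-group means from the ANCOVA estimate and covariance and refit the selected model to each draw with ED50 bounded above zero.

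A positive ED50 alone does not repair TD. Treat a draw that does not reach the target as 'not reached', rank it above all finite doses, report the share of such draws, and allow an open-ended upper limit. State that this rule overrides whatever the package function returns.

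In the same edit reconcile the maximum dose in ED_P (150 in Section 15, 450 among the doses in Shell Table 14.2.1.2.1) and the number of draws (10,000 in Section 15, 100,000 in the shell).

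The cost is a few sentences, a shell footnote and modest extra computing. Some intervals will be very wide or open-ended.

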'MOD' step [3] Selected Model xxxxxxxxx

Parameter	Estimate	95% CI of Estimate [6]
ED50	XX.X	[x.xx to x.xx]
ED90 [4]	XX.X	[x.xx to x.xx]
Asymptotic ED90 [5]	XX.X	[x.xx to x.xx]
Dose to achieve target (-1.25) effect	XX.X	[x.xx to x.xx]
Treatment effect at dose = 5 mcg	XX.X	[x.xx to x.xx]
Treatment effect at dose = 50 mcg	XX.X	[x.xx to x.xx]
Treatment effect at dose = 150 mcg	XX.X	[x.xx to x.xx]
Treatment effect at dose = 450 mcg	xx.x	[x.xx to x.xx]

CI: Confidence Interval; LOCF = Last Observation Carried Forward; MCP = Multiple Comparisons; Procedure; MOD = Modelling; NRS = Numeric rating scale.

Programming Notes:

• The 'MOD' step will only be performed if stage 4 is initiated, otherwise there would be insufficient dosing data to fit the non-linear models.

Final 1.0 | 12-Jul-2023 | Page 27 of 205

^[3] Results from the 'MOD' step will only be available in case any of the MCP tests is statistically significant.

^[4] ED90 = Effective Dose giving 90% of the effect of the maximum dose studied.

^[5] Asymptotic ED90 = Effective Dose giving 90% of the asymptotic maximum effect.

^{[6] 2.5%} and 97.5% quantiles taken from 100000 samples from the multivariate normal distribution for model fitted estimates and its covariance matrix. Reference Listing: 16.2.6.1

[figure not shown]

Table 14.2.1.2.2 Statistical Analysis of CFB to Week 12 Daily Pain NRS: Primary ANCOVA Analysis (LOCF) mITT Population

Model parameter estimates

					2-sided 95% unadjusted Asymmetric CL		2-sided
Parameter	Estimate	t value	Degrees of freedom	Standard Error	CL	[1]	P-value [2]
Intercept	XX.XX	XX.XX	•	xx.xxx	[x.xx to x.xx]		
Co-Medication Type			2				0.xxxx
Baseline pain NRS	XX.XX	XX.XX	1	XX.XXX	[x.xx to x.xx]		0.xxxx
Active 5 mcg vs Placebo	XX.XX	XX.XX	1	XX.XXX	[x.xx to x.xx]	[x.xx to x.xx]	0.xxxx
Active 150 mcg vs Placebo	XX.XX	XX.XX	1	XX.XXX	[x.xx to x.xx]	[x.xx to x.xx]	0.xxxx
Active 450 mcg vs Placebo	XX.XX	XX.XX	1	XX.XXX	[x.xx to x.xx]	[x.xx to x.xx]	0.xxxx
Model residual standard deviation	XX.XX						

ANCOVA = analysis of covariance; CFB = Change from Baseline;

CL = Confidence limits; LOCF = Last Observation Carried Forward; NRS = Numeric rating scale.

[2] P-value is derived from the following model: ANCOVA by dose using NRS baseline value and co-medication as covariates, with CFB to Week 12 (LOCF) as dependent variable.

Least Square Means

Treatment	Number of Subjects	LS mean [3]	95% CI of LS mean
Active 450 mcg	XX	X.XX	[x.xx to x.xx]
Active 150 mcg	XX	X.XX	[x.xx to x.xx]
Active 5 mcg	XX	X.XX	[x.xx to x.xx]
Placebo	XX	X.XX	[x.xx to x.xx]

[figure not shown]
CI = Confidence interval; LOCF = Last Observation Carried Forward; LS = least square; NRS = Numeric rating scale.

[3] The LS mean is a model estimate using fitted group parameter and the baseline weekly average pain NRS parameter evaluated at the grand mean over each group.

Reference Listing: 16.2.6.1

Final 1.0 | 12-Jul-2023 | Page 28 of 205

^[1] Lower limit of 1-sided 90% CL and upper limit of 1-sided 80% CL.

Programming Notes:

• Concomitant co-medication Type indicated for Painful Diabetic Neuropathy: either anticonvulsant class (pregabalin or gabapentin) or antidepressant class (duloxetine, venlafaxine, or amitriptyline).

• Rows for column dosing (column dosing will only be added if Stage 4 is initiated.

Final 1.0 | 12-Jul-2023 | Page 29 of 205

[figure not shown]

Table 14.2.1.3.1 Statistical Analysis of CFB Daily Pain NRS: MMRM Analysis. (Observed Cases) mITT Population

Model parameter estimates

[figure not shown]
					2-sided 95% unadjuste	d Asymmetric CL	2-sided
Parameter	Estimate	t value	Degrees of freedom	Standard Error	CL	[1]	P-value [2]
Intercept	XX.XX	XX.XX		XX.XXX			
Co-medication type			1				0.xxxx
Week			7				0.xxxx
Treatment			3				0.xxxx
Treatment*Week			21				0.xxxx
Baseline pain NRS	XX.XX	XX.XX	1	XX.XXX	[x.xx to x.xx]		0.xxxx
Active 5 mcg vs Placebo	XX.XX	XX.XX	1	XX.XXX	[x.xx to x.xx]	[x.xx to x.xx]	0.xxxx
Active 150 mcg vs Placebo	XX.XX	XX.XX	1	XX.XXX	[x.xx to x.xx]	[x.xx to x.xx]	0.xxxx
Active 450 mcg vs Placebo	XX.XX	XX.XX	1	XX.XXX	[x.xx to x.xx]	[x.xx to x.xx]	0.xxxx
Model residual standard deviation	xx.xx						

CFB = Change from Baseline; CL = Confidence limits; MMRM = Mixed Model for Repeated Measures; NRS = Numeric rating scale.

Final 1.0 | 12-Jul-2023 | Page 30 of 205

^[1] Lower limit of 1-sided 90% CL and upper limit of 1-sided 80% CL.

^[2] P-value is derived from the following model: MMRM using Time, Treatment, Treatment*Time, NRS baseline value, and Co-medication type as covariates, with CFB as dependent variable.

Least Square Means: week xxxxx

Treatment	Number of patients	LS mean [3]	95% CI of LS mean
Active 450 mcg	XX	X.XX	[x.xx to x.xx]
Active 150 mcg	xx	X.XX	[x.xx to x.xx]
Active 5 mcg	xx	X.XX	[x.xx to x.xx]
Placebo	XX	X.XX	[x.xx to x.xx]
Active 450 mcg - Placebo	XX	X.XX	[x.xx to x.xx]
Active 150 mcg - Placebo	XX	X.XX	[x.xx to x.xx]
Active 5 mcg - Placebo	xx	X.XX	[x.xx to x.xx]

CI = Confidence interval; LS = least square; NRS = Numeric rating scale.

Programming Notes:

- Include LSmeans and difference in Lsmean with Placebo in repeated tables for the Treatment*Week interaction.
- Rows for column dosing (column dosing will only be added if Stage 4 is initiated.

Final 1.0 | 12-Jul-2023 | Page 31 of 205

^[3] The LS mean is a model estimate using fitted group parameter and the baseline weekly average pain NRS parameter evaluated at the grand mean over each group. Reference Listing: 16.2.6.1

[figure not shown]

[figure not shown]

Table 14.2.1.3.2 Daily Pain NRS: Sensitivity of Primary MCP-Mod Analysis (BOCF) mITT Population

Programming Notes:

- Same shell as Table 14.2.1.2.1, substituting "LOCF = Last Observation Carried Forward" by "BOCF = Baseline Observation Carried Forward".
- The MCP-MOD approach will only be performed if stage 4 is initiated, otherwise there would be insufficient dosing data to fit the non-linear models.

Final 1.0 | 12-Jul-2023 | Page 32 of 205

[figure not shown]
4. Secondary Efficacy Analysis

Table 14.2.2.1
Galer NPS: Summary Statistics (Observed Cases)
mITT Population

Parameter: xxxxx					
	Placebo		MEDI7352		Total
Visit/		CCI	CCI	CCI	
Statistic	(N=xx)	(N=xx)	(N=xx)	(N=xx)	(N=xx)
Baseline [1]					
n	XX	XX	XX	XX	XX
Mean (SD)	xx.x (xx.xx)	xx.x (xx.xx)	xx.x(xx.xx)	xx.x (xx.xx)	xx.x (xx.xx)
Median	XX.X	XX.X	XX.X	XX.X	XX.X
Q1, Q3	XX.X, XX.X	XX.X, XX.X	XX.X, XX.X	XX.X, XX.X	XX.X, XX.X
Min, Max	xx, xx	xx, xx	xx, xx	xx, xx	XX, XX
Week 4					
n	XX	XX	XX	XX	XX
Mean (SD)	xx.x(xx.xx)	xx.x(xx.xx)	xx.x(xx.xx)	xx.x(xx.xx)	xx.x (xx.xx)
Median	XX.X	XX.X	XX.X	XX.X	XX.X
Q1, Q3	XX.X, XX.X	XX.X, XX.X	XX.X, XX.X	XX.X, XX.X	XX.X, XX.X
Min, Max	xx, xx	xx, xx	xx, xx	xx, xx	XX, XX
Week 4 CFB					
n	XX	XX	XX	XX	XX
Mean (SD)	xx.x (xx.xx)	xx.x (xx.xx)	xx.x(xx.xx)	xx.x (xx.xx)	xx.x (xx.xx)
Median	XX.X	XX.X	XX.X	xx.x	XX.X
Q1, Q3	xx.x, xx.x	xx.x, xx.x	XX.X, XX.X	xx.x, xx.x	XX.X, XX.X
Min, Max	XX, XX	xx, xx	xx, xx	xx, xx	xx, xx

•••

Final 1.0 | 12-Jul-2023 | Page 33 of 205

feel a single type of pain only sometimes

xx(xx.x%)

xx (xx.x%) xx (xx.x%)

xx(xx.x%)

For Pain Duration Frequency

Baseline [1]				
I feel a background pain all of the time and occasional flare-ups	xx (xx.x%)	xx (xx.x%)	xx (xx.x%)	xx (xx.x%)
I feel a single type of pain all the time	xx (xx.x%)	xx(xx.x%)	xx(xx.x%)	xx(xx.x%)

Week 4

CFB = Change from Baseline; n = number of subjects by treatment group at each visit for the parameter; N = number of subjects per treatment group; NPS = Neuropathic Pain Scale; SD = standard deviation; Q1 = first quartile; Q3 = third quartile.

xx(xx.x%)

xx (xx.x%)

xx (xx.x%)

Note: Data shown are Pain Intensity, Unpleasantness, and Descriptor scores on an 11-point (0-10) NRS, and Pain Duration/Frequency on a 3-point NRS (1-3), plus CFB for the same variables.

[1] Baseline is defined as the last observation recorded prior to the first dose of treatment.

Reference Listing: 16.2.6.2

Programming Notes:

- Include all observed data on Galer NPS scores for Baseline, Week 4, 8, 12, and 18.
- Repeat for the Parameters: Pain intensity, Pain Unpleasantness, Pain Sharpness, Pain Hotness, Pain Dullness, Pain Coldness, Pain Sensitivity, Pain Itching, Deep Pain Intensity, Surface Pain Intensity (All in an 11-point NRS), and Pain Duration/Frequency (in a 3-point NRS).
- A column for column dosing (column dosing (column dosing (column dosing (column dosing dosing dosing (column dosing dos

Final 1.0 | 12-Jul-2023 | Page 34 of 205

[figure not shown]

Table 14.2.2.2 Galer NPS: MMRM Analysis (Observed Cases) mITT Population

Model parameter estimates

[figure not shown]
					2-sided 95% unadjuste	ed Asymmetric CL	2-sided
Parameter	Estimate	t value	Degrees of freedom	Standard Error	CL	[1]	P-value [2]
Intercept	XX.XX	XX.XX	·	XX.XXX			
Co-Medication type			1				0.xxxx
Week			4				0.xxxx
Treatment			3				0.xxxx
Treatment*Week			12				0.xxxx
Baseline NPS	XX.XX	XX.XX	1	XX.XXX	[x.xx to x.xx]		0.xxxx
Active 5 mcg vs Placebo	XX.XX	XX.XX	1	XX.XXX	[x.xx to x.xx]	[x.xx to x.xx]	0.xxxx
Active 150 mcg vs Placebo	XX.XX	XX.XX	1	XX.XXX	[x.xx to x.xx]	[x.xx to x.xx]	0.xxxx
Active 450 mcg vs Placebo	XX.XX	XX.XX	1	XX.XXX	[x.xx to x.xx]	[x.xx to x.xx]	0.xxxx
Model residual standard deviation	xx.xx						

CFB = Change from Baseline; CL = Confidence limits; MMRM: Mixed Model for Repeated Measures; NPS = Neuropathic Pain Scale.

Final 1.0 | 12-Jul-2023 | Page 35 of 205

^[1] Lower limit of 1-sided 90% CL and upper limit of 1-sided 80% CL.

^[2] P-value is derived from the following model: MMRM using Time, Treatment, Treatment*Time, NPS baseline value, and Co-medication type as covariates, with CFB as dependent variable.

Least Square Means: week: xxxx

Treatment	Number of patients	LS mean [3]	95% CI of LS mean
Active 450 mcg	XX	X.XX	[x.xx to x.xx]
Active 150 mcg	XX	X.XX	[x.xx to x.xx]
Active 5 mcg	XX	X.XX	[x.xx to x.xx]
Placebo	XX	X.XX	[x.xx to x.xx]
Active 450 mcg - Placebo	XX	X.XX	[x.xx to x.xx]
Active 150 mcg - Placebo	XX	X.XX	[x.xx to x.xx]
Active 5 mcg - Placebo	XX	X.XX	[x.xx to x.xx]

CI = Confidence interval; LS = least square; NPS = Neuropathic Pain Scale.

Programming Notes:

- Include Lsmeans and difference in Lsmean with Placebo in repeated tables for the Treatment*Week interaction.
- Include all observed data on Galer NPS scores for Baseline, Week 4, 8, 12, and 18.
- Analysis is done for Galer NPS Total Score.
- Rows for column dosing (column dosing will only be added if Stage 4 is initiated.

Final 1.0 | 12-Jul-2023 | Page 36 of 205

^[3] The LS mean is a model estimate using fitted group parameter and the baseline NPS parameter evaluated at the grand mean over each group. Reference Listing: 16.2.6.2

[figure not shown]

Table 14.2.3.1
DSIS: Summary Statistics (Observed Cases)
mITT Population

	Placebo		MEDI7352		Total
Visit/ Statistic	(N=xx)	(N=xx)	(N=xx)	(N=xx)	(N=XX)
	(= : ====)	(= : ===)	(= : :::)	(= : ::::)	(= - = -)
Baseline [1]					
n	XX	XX	XX	XX	XX
Mean (SD)	xx.x (xx.xx)	xx.x(xx.xx)	xx.x(xx.xx)	xx.x(xx.xx)	xx.x (xx.xx)
Median	XX.X	XX.X	XX.X	XX.X	XX.X
Q1, Q3	XX.X, XX.X				
Min, Max	XX, XX				
Week 4					
n	XX	XX	XX	XX	XX
Mean (SD)	xx.x (xx.xx)	xx.x(xx.xx)	xx.x(xx.xx)	xx.x(xx.xx)	xx.x (xx.xx)
Median	XX.X	XX.X	XX.X	XX.X	XX.X
Q1, Q3	XX.X, XX.X				
Min, Max	XX, XX				
Week 4 CFB					
n	XX	XX	XX	XX	XX
Mean (SD)	xx.x (xx.xx)				
Median	XX.X	XX.X	XX.X	XX.X	XX.X
Q1, Q3	xx.x, xx.x				
Min, Max	xx, xx				

[figure not shown]
CFB = Change from Baseline; DSIS = Daily Sleep Interference; n = number of subjects by treatment group at each visit for the parameter; N = number of subjects per treatment group; SD = standard deviation; Q1 = first quartile; Q3 = third quartile.

Note: Data shown are weekly averages of the average daily sleep interference scores on an 11-point (0-10) NRS and CFB for the same variable.

[1] Baseline is defined as the average of the 'non-missing' DSIS within the seven-day period prior to randomization i.e., Day -7 to Day -1, inclusive.

Reference Listing: 16.2.6.3

Final 1.0 | 12-Jul-2023 | Page 37 of 205

Programming Notes:

- Include all observed data on weekly averages of the average daily Sleep Interference score for Baseline, Week 4, 8, 12, and 18.
- A column for column

Final 1.0 | 12-Jul-2023 | Page 38 of 205

[figure not shown]

Table 14.2.3.2 DSIS: MMRM Analysis (Observed Cases) mITT Population

Model parameter estimates

[figure not shown]
					2-sided 95% unadjuste	d Asymmetric CL	2-sided
Parameter	Estimate	t value	Degrees of freedom	Standard Error	CL	[1]	P-value [2]
Intercept	XX.XX	XX.XX		XX.XXX			
Co-medication type			1				0.xxxx
Week			4				0.xxxx
Treatment			3				0.xxxx
Treatment*Week			12				0.xxxx
Baseline DSIS	XX.XX	XX.XX	1	XX.XXX	[x.xx to x.xx]		0.xxxx
Active 5 mcg vs Placebo	XX.XX	XX.XX	1	XX.XXX	[x.xx to x.xx]	[x.xx to x.xx]	0.xxxx
Active 150 mcg vs Placebo	XX.XX	XX.XX	1	XX.XXX	[x.xx to x.xx]	[x.xx to x.xx]	0.xxxx
Active 450 mcg vs Placebo	XX.XX	XX.XX	1	XX.XXX	[x.xx to x.xx]	[x.xx to x.xx]	0.xxxx
Model residual standard deviation	xx.xx						

CFB = Change from Baseline; CL = Confidence limits; MMRM: Mixed Model for Repeated Measures; DSIS = Daily Sleep Interference.

Final 1.0 | 12-Jul-2023 | Page 39 of 205

^[1] Lower limit of 1-sided 90% CL and upper limit of 1-sided 80% CL.

^[2] P-value is derived from the following model: MMRM using Time, Treatment, Treatment*Time, DSIS baseline value, and Co-medication type as covariates, with CFB as dependent variable.

Least Square Means: week xxxx

Treatment	Number of patients	LS mean [3]	95% CI of LS mean
Active 450 mcg	xx	X.XX	[x.xx to x.xx]
Active 150 mcg	XX	X.XX	[x.xx to x.xx]
Active 5 mcg	XX	X.XX	[x.xx to x.xx]
Placebo	XX	X.XX	[x.xx to x.xx]
Active 450 mcg - Placebo	XX	X.XX	[x.xx to x.xx]
Active 150 mcg - Placebo	XX	X.XX	[x.xx to x.xx]
Active 5 mcg - Placebo	XX	X.XX	[x.xx to x.xx]

CI = Confidence interval; LS = least square.

Programming Notes:

- Include LS means and difference in LS mean with Placebo in repeated tables for the Treatment*Week interaction.
- Include all observed data on weekly average DSIS for Baseline, Week 4, 8, 12, and 18.
- Rows for column dosing (column dosing will only be added if Stage 4 is initiated.

Final 1.0 | 12-Jul-2023 | Page 40 of 205

^[3] The LS mean is a model estimate using fitted group parameter and the baseline weekly average DSIS parameter evaluated at the grand mean over each group. Reference Listing: 16.2.6.1

[figure not shown]

[figure not shown]
Table 14.2.4.1 SF-36: Summary Statistics (Observed Cases) mITT Population

Parameter: xxxxx

Parameter: xxxxx	Placebo		MEDI7352		Total
Visit/		CCI	CCI	CCI	-
Statistic	(N=xx)	(N=xx)	(N=xx)	(N=xx)	(N=XX)
Baseline [1]					
n	XX	XX	XX	XX	XX
Mean (SD)	xx.x (xx.xx)	xx.x(xx.xx)	xx.x(xx.xx)	xx.x (xx.xx)	xx.x (xx.xx)
Median	XX.X	XX.X	XX.X	XX.X	XX.X
Q1, Q3	XX.X, XX.X	XX.X, XX.X	XX.X, XX.X	XX.X, XX.X	XX.X, XX.X
Min, Max	xx, xx	xx, xx	xx, xx	XX, XX	xx, xx
Week 12					
n	XX	XX	XX	XX	XX
Mean (SD)	xx.x (xx.xx)	xx.x(xx.xx)	xx.x(xx.xx)	xx.x (xx.xx)	xx.x (xx.xx)
Median	XX.X	XX.X	XX.X	XX.X	XX.X
Q1, Q3	XX.X, XX.X	XX.X, XX.X	XX.X, XX.X	XX.X, XX.X	XX.X, XX.X
Min, Max	xx, xx	xx, xx	xx, xx	XX, XX	xx, xx
Week 12 CFB					
n	XX	XX	XX	XX	XX
Mean (SD)	xx.x (xx.xx)	xx.x(xx.xx)	xx.x(xx.xx)	xx.x(xx.xx)	xx.x (xx.xx)
Median	xx.x	XX.X	XX.X	XX.X	XX.X
Q1, Q3	xx.x, xx.x	XX.X, XX.X	XX.X, XX.X	XX.X, XX.X	XX.X, XX.X
Min, Max	xx, xx	XX, XX	xx, xx	XX, XX	XX, XX

•••

Final 1.0 | 12-Jul-2023 | Page 41 of 205

When parameter is "Change in general Health"

Baseline [1]

Much better now than one year ago	xx (xx.x%)	xx (xx.x%)	xx(xx.x%)	xx(xx.x%)	xx (xx.x%)
Somewhat better now than one year ago	xx (xx.x%)	xx(xx.x%)	xx(xx.x%)	xx (xx.x%)	xx (xx.x%)
About the same as one year ago	xx (xx.x%)	xx (xx.x%)	xx(xx.x%)	xx(xx.x%)	xx (xx.x%)
Somewhat worse now than one year ago	xx(xx.x%)	xx(xx.x%)	xx (xx.x%)	xx(xx.x%)	xx (xx.x%)
Much worse now than one year ago	xx(xx.x%)	xx(xx.x%)	xx (xx.x%)	xx(xx.x%)	xx (xx.x%)

Week 12

CFB = Change from Baseline; n = number of subjects by treatment group at each visit for the parameter; N = number of subjects per treatment group; NRS = numeric rating scale; SD = standard deviation; SF-36 = 36-Item Short-Form Health Survey; Q1 = first quartile; Q3 = third quartile.

Note: Data shown are derived SF-36 scores and Change in General Health on a 5-point NRS (1-5), plus CFB for the same variables.

[1] Baseline is defined as the last observation recorded prior to the first dose of treatment.

Reference Listing: 16.2.6.4

Programming Notes:

- Include all observed data on SF-36 scores for Baseline and Week 12.
- Repeat for the Parameters: Physical functioning, Role limitations due to physical health, Role limitations due to emotional problems, Vitality (Energy/fatigue), Emotional well-being, Social functioning, Pain and General Health (from 0 to 100), Physical Health Summary, Mental Health Summary, and Change in general Health (in a 5-point NRS).
- A column for column dosing (column dosing will only be added if Stage 4 is initiated.

Final 1.0 | 12-Jul-2023 | Page 42 of 205

[figure not shown]

Table 14.2.4.2 SF-36: MMRM Analysis (Observed Cases) mITT Population

Model parameter estimates: xxxxxxxx

[figure not shown]
					2-sided 95% unadjuste	d Asymmetric CL	2-sided
Parameter	Estimate	t value	Degrees of freedom	Standard Error	CL	[1]	P-value [2]
Intercept	XX.XX	XX.XX		XX.XXX			
Co-medication type			XX				0.xxxx
Week			1				0.xxxx
Treatment			3				0.xxxx
Treatment*Week			3				0.xxxx
Baseline SF-36	XX.XX	XX.XX	1	XX.XXX	[x.xx to x.xx]		0.xxxx
Active 5 mcg vs Placebo	XX.XX	XX.XX	1	XX.XXX	[x.xx to x.xx]	[x.xx to x.xx]	0.xxxx
Active 150 mcg vs Placebo	XX.XX	XX.XX	1	XX.XXX	[x.xx to x.xx]	[x.xx to x.xx]	0.xxxx
Active 450 mcg vs Placebo	XX.XX	XX.XX	1	XX.XXX	[x.xx to x.xx]	[x.xx to x.xx]	0.xxxx
Model residual standard deviation	xx.xx						

CFB = Change from Baseline; CL = Confidence limits; MMRM: Mixed Model for Repeated Measures; SF-36 = 36-Item Short-Form Health Survey.

Final 1.0 | 12-Jul-2023 | Page 43 of 205

^[1] Lower limit of 1-sided 90% CL and upper limit of 1-sided 80% CL.

^[2] P-value is derived from the following model: MMRM using Time, Treatment, Treatment*Time, SF-36 baseline value, and Co-medication type as covariates, with CFB as dependent variable.

Least Square Means: xxxxxxxx / week xxxx

Treatment	Number of patients	LS mean [3]	95% CI of LS mean
Active 450 mcg	xx	X.XX	[x.xx to x.xx]
Active 150 mcg	xx	X.XX	[x.xx to x.xx]
Active 5 mcg	xx	X.XX	[x.xx to x.xx]
Placebo	xx	X.XX	[x.xx to x.xx]
Active 450 mcg - Placebo	xx	X.XX	[x.xx to x.xx]
Active 150 mcg - Placebo	xx	X.XX	[x.xx to x.xx]
Active 5 mcg - Placebo	XX	X.XX	[x.xx to x.xx]

CI = Confidence interval; LS = least square.

Programming Notes:

- Include Lsmeans and difference in Lsmean with Placebo in repeated tables for the Treatment*Week interaction.
- Include all observed data on SF-36 scores for Baseline and Week 12.
- Repeat for the Parameters: Physical functioning, Role limitations due to physical health, Role limitations due to emotional problems, Vitality (Energy/fatigue), Emotional well-being, Social functioning, Pain and General Health. Add parameter name after 'Model parameter estimates:' and after 'Least Square Means:'
- Rows for column dosing (column dosing will only be added if Stage 4 is initiated.

Final 1.0 | 12-Jul-2023 | Page 44 of 205

^[3] The LS mean is a model estimate using fitted group parameter and the baseline SF-36 parameter evaluated at the grand mean over each group. Reference Listing: 16.2.6.4

[figure not shown]
[figure not shown]

Table 14.2.5.1 Rescue Medication Use: Summary Statistics mITT Population

Variable	Placebo		MEDI7352		
Statistic or Category	(N=xx)	CCI (N=xx)	(N=xx)		
Statistic of Category	(11-XX)	(11-11)	(N=xx)	(N=xx)	(11-XX)
